7.1.1 Events not Qualifying as AEs/SAEs

The following are not considered to be AEs or SAEs:

- Medical or surgical procedures (e.g., endoscopy, appendectomy). The condition that leads to the procedure is considered the AE.
- Elective procedures, planned hospitalizations, and procedures for treatment of conditions noted in the subject's medical history (present prior to signing the ICF) that have not worsened are not considered AEs.
- Situations where an untoward medical occurrence did not occur (i.e., admission to hospital for social circumstances).
- Anticipated day-to-day fluctuations of pre-existing medical conditions that were present at start of study. These conditions are considered part of the subject's medical history and must be adequately documented on the appropriate page of the eCRF.
- Clear progression of disease under study should not be reported as an AE or SAE unless the investigator considers the progression of underlying neoplasia to be atypical in its nature, presentation, or severity from the normal course of the disease in a particular subject. Signs and symptoms that are clearly consistent with the expected progression of the underlying cancer should not be reported as an AE, and hospitalizations due to the progression of cancer do not necessarily qualify for an SAE. Deaths that are clearly determined to be due to disease progression should not be reported as AEs/SAEs.
- In the case where the medical condition is known when the subject enters the trial, only worsening (increased frequency or intensity of the episodes or attacks) will be documented as an AE. If the medical condition is detected during the trial, and if repeated

episodes enable diagnosis of a chronic disease, the episodes will be grouped together in the eCRF, and the diagnosis will be clearly described.

- Laboratory abnormalities: An isolated, out-of-range laboratory result in the absence of any associated clinical finding may or may not be considered an AE; the investigator's evaluation should be based on a consideration of the overall clinical context.

7.2 Classification of an Adverse Event

All measures required for AE management and the ultimate outcome of the event will be recorded in the source document and reported to the Sponsor.

7.2.1 Assessment of Severity

The descriptions and grading scales found in the revised NCI-CTCAE version 5.0 will be utilized for AE reporting. A copy of these criteria can be downloaded from the website: https://ctep.cancer.gov/protocoldevelopment/electronic_applications/ctc.htm.

For AEs not included in the NCI-CTCAE v5.0 grading system, the following guidelines will be used to describe severity:

- Grade 1: mild
- Grade 2: moderate
- Grade 3: severe
- Grade 4: life-threatening
- Grade 5: death

NOTE: A distinction should be drawn between serious and severe AEs. Severity is an estimate or measure of the intensity of an AE, while the criteria for serious AEs are indications of adverse subject outcomes for regulatory reporting purposes. A severe AE need not necessarily be considered serious, and a serious AE need not be considered severe.

7.2.2 Assessment of Causality

The clinician's assessment of an AE's relationship to study treatment is part of the documentation process, but it is not a factor in determining what is or is not reported in the study. If there is any doubt as to whether a clinical observation is an AE, the event should be reported. All AEs must have their relationship to the administered treatment (SL-172154 and PLD or MIRV) assessed. In a clinical trial, the drug(s) being administered must always be suspect. Investigators should consider alternative causes such as natural history of the underlying disease, concomitant medications, comorbidities, and other risk factors when making an assessment.

To help assess causality, the following guidelines are used.

- **Related** – There is reasonable causal relationship between the IP(s) being administered and the AE. The event responds to interruption of study drug and recurs with re-challenge, when clinically feasible.

- **Possibly Related** - There is reasonable causal relationship between the IP(s) being administered and the AE. Information on whether the event responds to interruption of administered treatment and/or re-challenge is lacking or unclear.
- **Unlikely Related** - There is a temporal relationship to administration of the IP(s) in the study, but there is not a reasonable causal relationship between the IP(s) being administered and the AE (i.e., the AE is doubtfully related to SL-172154, PLD, or MIRV).
- **Not Related** – There is not a temporal relationship to administration of the IP(s) in the study (e.g., too early, too late, or SL-172154, PLD or MIRV not taken), or there is a reasonable causal relationship between another drug, concurrent disease, or circumstance and the AE.

7.2.3 Expectedness

The Sponsor will be responsible for determining whether an AE is expected or unexpected.

- **Unexpected** - An AE will be considered unexpected if the nature, severity, or frequency of the event is not consistent with the safety information in Guidance for Investigators of the current SL-172154 IB or MIRV IB and the current PLD prescribing information. "Unexpected," as used in this definition, also refers to AEs or ARs that are mentioned in the IB or prescribing information as occurring with a class of drugs or as anticipated from the pharmacological properties of the drug not specifically mentioned as occurring with SL-172154, MIRV or PLD.
- **Expected** - AEs that are common and known to occur for SL-172154, MIRV or PLD. Expectedness refers to the awareness of AEs previously observed, not on what might be anticipated from the properties of SL-172154, MIRV and PLD.

7.3 Timing for Event Assessment and Follow-Up

All AEs occurring while on study must be documented appropriately regardless of relationship. All AEs will be followed to adequate resolution. The occurrence of an AE or SAE may come to the attention of study personnel during study visits and interviews of a study subject presenting for medical care, or upon review by a study monitor.

Any medical condition that is present at the time that the subject is screened will be considered as baseline (e.g., medical history) and not reported as an AE.

7.4 Procedures for Recording and Reporting of Adverse Events

Event	Reporting Procedures
Adverse Event	Subjects will be followed continuously for AEs during the study and for 30 days after the last dose of SL-172154. After a subject is discontinued from SL-172154 due to progressive disease or for other reasons, any ongoing AE should be followed until resolution (or return to baseline) and documented in the eCRF, regardless of whether the event(s) is attributed to trial medication. If another anti-cancer agent is started within 30 days of the last dose of SL-172154, only AEs and SAEs that occur before the new anticancer therapy should be recorded. The following information will be recorded: description, date of onset and end date, severity, assessment of relatedness to trial medication, and action taken. Follow-up

Event	Reporting Procedures
	
information should be provided, as necessary. AEs will be followed either until resolution, or the event is considered stable.
 
It will be left to the investigator's clinical judgment to decide whether an AE is of sufficient severity to require the subject's removal from study treatment. A subject may also voluntarily withdraw from study treatment due to what he or she perceives as an intolerable AE. If either of these occurs, the subject must undergo an end of treatment assessment and be given appropriate care under medical supervision until symptoms cease or the condition becomes stable.

Serious Adverse Event	
The study clinician will complete a SAE Form within the following timelines:
 
• All deaths and immediately life-threatening events meeting the SAE criteria (as outlined in Section 7.1), whether related or unrelated, will be recorded on the SAE Form and submitted to the study Sponsor or designee within 24 hours of site awareness.• Other SAEs regardless of relationship, will be submitted to the study Sponsor or designee within 24 hours of site awareness. 
All SAEs will be followed until satisfactory resolution or until the site investigator deems the event to be chronic or the adherence to be stable. Other supporting documentation of the event may be requested by the Sponsor and should be provided as soon as possible. The Sponsor will be responsible for notifying Regulatory Authorities of any unexpected fatal or life-threatening suspected adverse reaction (AR) as soon as possible but in no case later than 7 calendar days after the Sponsor's initial receipt of the information. The Sponsor will be responsible for notifying Regulatory Authorities of any other serious unexpected suspected adverse reaction as soon as possible but in no case later than 15 calendar days after the Sponsor's initial receipt of the information.
 
Sponsor Contact Information for SAE Reporting [REDACTED]

7.5 Reporting of Pregnancy

Although not an AE in and of itself, pregnancy as well as its outcome must be documented via the Pregnancy Report Form provided by the Sponsor. Any pregnancy occurring in a subject or subject's partner from the time of consent to 30 days after the last dose of SL-172154 must be reported and then followed for outcome. Newborn infants born to the subject or subject's partner should be followed until 30 days old.

FCBP must discontinue study treatment immediately if they become pregnant during the study. To ensure subject safety, each pregnancy must be reported to the Sponsor within two weeks of learning of its occurrence. The pregnancy must be followed to determine outcome (including premature termination) and status of mother and child. Pregnancy complications and elective terminations for medical reasons must be reported as a SAE. Spontaneous abortions must be reported as a SAE.

Any SAE occurring in association with a pregnancy and brought to the investigator's attention after the subject has discontinued study treatment must be promptly reported to the Sponsor.

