3.11 Study Treatment Discontinuation Criteria

A subject will receive the assigned study treatment (e.g., SL-172154 and PLD or SL-172154 and MIRV) until any of the following events occur during the study:

- Documented disease progression (radiological or clinical)
- A subject suffers an AE that, in the judgement of the investigator, Sponsor, or Medical Monitor, presents an unacceptable risk to the subject
- General or specific changes in the subject's condition (e.g., a significant intercurrent illness or complication) that, in the judgement of the investigator, are unacceptable for further administration of study treatment
- Subject decides to discontinue further study treatment
- Occurrence of pregnancy
- Significant non-compliance with protocol requirements
- Death
- Termination of the study by Sponsor

If one agent in the assigned regimen is permanently discontinued for any reason, at the investigator's discretion, the subject may continue to receive the other agent in the assigned regimen as monotherapy until meeting one of study treatment discontinuation criteria.

In the event of permanent discontinuation of all study treatment, subjects should be strongly encouraged to complete all scheduled assessments at the PTV and the SFU contacts.

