- i. **Pregnancy Test:** A serum pregnancy test (beta-human chorionic gonadotropin [β -hCG]) or urine pregnancy test must be performed at screening for all FCBP within 4 days of the first dose of PLD on Cycle 1 Day 1. Repeat this test every 8 weeks during study treatment (i.e., C3D1, C5D1, C7D1, etc.) and at PTV. Contraception should be continued for at least 6 months (or for the duration required by local regulatory guidance) after the last dose of PLD or 3 months after the last dose of SL-172154, whichever is longer.
- j. **Hematology/ Clinical Chemistry/ Coagulation/ TSH/ Free T4/ Antiviral Testing:** will be performed at local laboratories according to the laboratory's normal procedures. Laboratory tests required are provided in Section 6.5.9.
- k. **Pharmacokinetic (PK) / Anti-Drug Antibody (ADA):** Blood sample collection timings for SL-172154 PK/ADA measurement are outlined in Section 6.1.1. Blood volumes required will be provided in the Study Lab Manual (SLM). PK/ADA samples should not be collected from infusion port for drug delivery i.e., recommend having a separate line in the opposite arm for sample collection.
 1. If a subject discontinues SL-172154 due to IRR and continues on PLD monotherapy, to the extent feasible, an additional ad-hoc ADA sample should be collected at a subsequently scheduled visit.
 2. All subjects should have just one additional blood sample collected for SL-172154 ADA assessment within 45-90 days of last dose of SL-172154 study treatment.
- l. **Cytokines and Receptor Occupancy:** Blood sample collection timing for cytokine and receptor occupancy assessments are outlined in Section 6.1.1. Blood volumes required will be provided in the SLM. Cytokine samples should not be collected from infusion port for drug delivery i.e., recommend having a separate line in the opposite arm for sample collection.

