h.	
Physical Examination: A full physical exam is required only at screening and PTV. Physical exams should be performed per standard of care during the on-treatment period.

i.	
Vital Signs and Pulse Oximetry: Blood pressure (BP), heart rate (HR), temperature (T) and respiratory rate (RR) must be measured after the subject has been sitting for at least five minutes (min). Pulse oximetry will be collected to coincide with vital sign time points noted below.
 
1. Collect vital signs/pulse oximetry on Day 1 of every Cycle at Predose (within 60 min of starting the MIRV infusion); postinfusion vital signs should be collected as clinically indicated for potential infusion-related reaction.2. Collect vital signs/pulse oximetry during Cycle 1 on Day 8 and Day 15: Predose (within 60 min of starting the SL-172154 infusion), at the end of infusion (EOI; \pm 5 min) and then 0.5 hour [hr] (\pm 5 min), 2 hr (\pm 10 min), and 4 hr (\pm 10 min) after end of infusion (EOI) of SL-172154.3. Collect vital signs/pulse oximetry on Day 8 and Day 15 of Cycle 2 and in each subsequent cycle: Predose (within 60 min of starting the infusion) and at the end of infusion [EOI] (\pm 5 min) of SL-172154.4. For subjects experiencing any grade IRR, refer to Section 3.7.1.1 for schedule of vital signs that should be measured at time of the IRR event.
j.	
Ocular Symptom Assessment: will be performed by the treating physician or other qualified individual before the start of each cycle for all subjects. For subjects receiving MIRV reporting new CTCAE $>$ Grade 1 ocular symptoms, treatment will be held until the subject is evaluated by an eye care professional for a complete examination. Refer to Table 8 and Table 9 for additional details on management of ocular findings on study.

k.	
Pregnancy Test: A serum pregnancy test (beta-human chorionic gonadotropin [β-hCG]) or urine pregnancy test must be performed at screening for all FCBP within 4 days of the first dose of MIRV on Cycle 1 Day 1. Repeat this test every 6 weeks during study treatment (i.e., C3D1, C5D1, C7D1, etc.) and at PTV. Contraception should be continued for at least 3 months after the last dose of either SL-172154 or MIRV.

l.	
Hematology/ Clinical Chemistry/ Coagulation/ TSH/ Free T4/ Antiviral Testing: will be performed at local laboratories according to the laboratory's normal procedures. Required laboratory tests are provided in Section 6.5.9.

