†Abstinence (relative to heterosexual activity) can be used as the sole method of contraception if it is: (1) consistently employed during the entire period of risk associated with the administered drugs; (2) consistent with the subject's preferred and usual lifestyle; and (3) considered acceptable by local regulatory agencies and IRBs/IECs. Periodic abstinence (e.g., calendar, ovulation, sympto-thermal, postovulation methods) and withdrawal are not acceptable methods of contraception.

‡If a contraceptive method listed above is restricted by local regulations/guidelines, then it does not qualify as an acceptable method of contraception for subjects participating at sites in this country/region.

Subjects should be informed that taking SL-172154, PLD, or MIRV may involve unknown risks to the fetus (unborn baby) if pregnancy were to occur during the study. To participate in the study, subjects of childbearing potential must adhere to the contraception requirement (described above) starting at least 14 days prior to the first dose of study treatment, during treatment, and through at least 6 months (or for the duration required by local regulatory guidance) after the last dose of PLD or at least 3 months after the last dose of MIRV or SL-172154, whichever is longer.

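### Section 7.5's explicit pregnancy-reporting window ends 30 days after the last SL-172154 dose, short of the protocol's own post-treatment contraception period and possibly while PLD or MIRV is still being given

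*Protocol*

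**What the plan says.** Section 7.5 has three parts that bear on this point.

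- Its first paragraph sets the only dated window. A pregnancy in a subject or in her partner falls under it "from the time of consent to 30 days after the last dose of SL-172154 must be reported". The outcome must also be tracked, and newborns followed to 30 days of age.
- Its second paragraph opens with pregnancy arising during the study. It gives the site two weeks from learning of any pregnancy to tell the sponsor, and asks for follow-up of the outcome and of mother and child. No 30-day limit appears. Pregnancy complications, spontaneous abortions and medically indicated terminations are to be reported as SAEs.
- Its third paragraph covers late events: "Any SAE occurring in association with a pregnancy" that comes to the investigator's attention after treatment has stopped must be reported promptly. Again there is no end date.

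The contraception rules are longer. Appendix 16.2 runs them "through at least 6 months (or for the duration required by local regulatory guidance) after the last dose of PLD". For the other two drugs its minimum is 3 months, and the longer period governs. Inclusion criterion 14 in section 4.1 sets the same minimum periods. So do the pregnancy-test footnotes of the schedules: section 6.1 says "Contraception should be continued for at least 6 months" after PLD, and section 6.2 says "Contraception should be continued for at least 3 months after the last dose of either SL-172154 or MIRV". The same paragraph of Appendix 16.2 warns that all three drugs "may involve unknown risks to the fetus (unborn baby) if pregnancy were to occur during the study".

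Section 3.11 adds that if one agent is stopped for good, "the subject may continue to receive the other agent in the assigned regimen as monotherapy".

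**The concern.** Two features of the dated window stand out.

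First, its length. The protocol asks subjects to avoid pregnancy for 3 to 6 months after treatment, but its one explicit reporting window lasts 30 days.

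Second, its anchor. The clock starts at the last dose of SL-172154 alone. When PLD or MIRV continues as a single agent, the clock can run out during treatment with a cytotoxic drug or a cytotoxic conjugate. Sections 6.1 and 6.2 still require pregnancy tests every 8 weeks (PLD) or 6 weeks (MIRV) during study treatment and at the post-treatment visit. A scheduled test could then detect a pregnancy that, on the first paragraph of 7.5, nobody has to report.

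At stake are exposure and outcome data for two combinations that section 1.7.1 says had not previously been studied in humans. A site that follows the explicit limit would not file a report on an uneventful pregnancy conceived after the window closed.

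**Working it through.** The plan gives no figure of its own to reproduce. The check sets the windows side by side.

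**Inputs**
- Reporting window: 30 days after the last SL-172154 dose (7.5).
- Contraception: at least 3 months after SL-172154 or MIRV, at least 6 months after PLD (4.1, 6.1, 6.2, 16.2).
- Dosing days: PLD or MIRV on Day 1, SL-172154 on Days 8 and 15 (3.1).
- Month length: 30.4375 days (SAP 5.3.3), so 3 months = 91.3 days and 6 months = 182.6 days.

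**Full final cycle.** The last partner dose is on Day 1 and the last SL-172154 dose on Day 15, 14 days later. The window therefore closes 14 + 30 = 44 days after the partner dose. Share outside = 1 − (days covered ÷ contraception period).

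| Counted from last dose of | Period (days) | Covered (days) | Outside |
|---|---|---|---|
| PLD | 182.6 | 44 | 1 − 44/182.6 = 76% |
| MIRV | 91.3 | 44 | 1 − 44/91.3 = 52% |
| SL-172154 | 91.3 | 30 | 1 − 30/91.3 = 67% |

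In the PLD regimen the 6 months after PLD govern. Seen from the last SL-172154 dose, 182.6 − 14 = 168.6 days of contraception remain. Of these, 138.6 (82%) lie beyond the window.

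**Partner drug continued alone.** If the last PLD or MIRV dose falls g months after the last SL-172154 dose, the window closes 30.4375 × g − 30 days before that last partner dose.
- g = 1: 0.4 days before
- g = 2: 30.9 days before
- g = 4: 91.8 days before

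The values of g are assumptions, since the documents do not say how long single-agent treatment might last. From about one month on, the partner drug's whole post-dose period lies outside the window.

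**Time on treatment included.** Suppose all drugs end on the same day, contraception starts 14 days before the first dose (16.2), and treatment lasts 4 months (assumed).
- MIRV regimen: (91.3 − 30) ÷ (14 + 121.75 + 91.3) = 27% outside
- PLD regimen: (182.6 − 30) ÷ (14 + 121.75 + 182.6) = 48% outside

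For 1 to 12 months on treatment, the shares run from 45% down to 13% (MIRV) and from 67% down to 27% (PLD).

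**The case against.** **The two durations are different rules.** No passage says that they must match, and a site can comply with both. Thirty days is also the protocol's AE collection window. This stands as far as it goes: the length of the window is a choice, not a logical contradiction with Appendix 16.2. It does not defend the anchor. The protocol already varies there: the AE footnote in 6.1 and section 7.4 count from SL-172154, while the AE footnote in 6.2 counts from study treatment.

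**Section 7.5 has more than one backstop.** A reader might infer that only the late-SAE clause reaches beyond 30 days. The text does not support that. The second paragraph asks for every pregnancy, with outcome, once the site learns of it. It begins with pregnancy during the study, and section 3.12 follows subjects until death or study end, so it can be read to cover late cases. Adverse outcomes are reportable as SAEs in any case. This narrows the loss to uncomplicated pregnancies and their outcomes, and to pregnancies nobody mentions. It also shows that 7.5 can be read two ways, and a site may reasonably follow the explicit limit.

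**The fetal-risk sentence speaks of pregnancy during the study.** Taken alone, it does not establish a risk period of 3 or 6 months after treatment. The comparison here is therefore with the contraception period, which is stated outright.

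**Few subjects are affected.** Appendix 16.2 removes women with prior bilateral oophorectomy, bilateral salpingectomy or hysterectomy from the childbearing-potential group, and section 1.2 describes debulking surgery as part of front-line care. This stands. Section 1.4.7 also reports an SL-172154 serum half-life below 1 hour, but that says nothing about PLD or MIRV, and section 5.1.6 notes that pharmacologic effect could outlast detectable drug.

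**Conclusion.** The point holds as a gap and an internal inconsistency in section 7.5. The explicit window is tied to one of the two drugs each subject receives, and it can lapse while the other is still being given. After a full final cycle it leaves about 76% (PLD), 52% (MIRV) and 67% (SL-172154) of the respective post-treatment contraception periods uncovered. These shares assume the Day 1 / Day 15 schedule was completed and take the contraception minimums at face value.

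A reader might go further and infer that most of the whole risk period is unreported. The documents do not support that, because pregnancies from consent onward are reportable while SL-172154 continues. With an assumed 4 months on treatment, the uncovered share is 27% (MIRV) or 48% (PLD). Nor should one take 30 of 183 days as the typical cover after PLD. That figure needs both drugs to end on the same day, which the schedule does not plan.

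The practical effect is small: few subjects of childbearing potential, and adverse pregnancy outcomes reportable anyway. The documents give no count from which to estimate a number. No objective or outcome measure in section 2 depends on these data. It is worth correcting because the passages need reconciling and the change is cheap.

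**What to change.** In section 7.5, reconcile the first two paragraphs. State one window for both reporting and outcome follow-up: from consent to the end of the contraception period already given in 4.1 and 16.2, counted from the last dose of whichever study drug gives the later date. The contraception periods themselves do not change.

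For subjects of childbearing potential, add a question about pregnancy at the existing survival contacts wherever the subject herself is reached. Contacts run every 3 months from the post-treatment visit, which is about 30 days after the last dose. The first two therefore fall at about 30 + 91 = 121 and 30 + 183 = 213 days, beyond the 3-month and 6-month periods respectively.

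The cost is one sentence and one question, with no added visit or test. There are two downsides. Reporting obligations last somewhat longer, and follow-up of a late pregnancy could run up against the end of the study. Capture will also be incomplete, because sections 6.1 and 6.2 allow survival status to be taken from chart review or an obituary notice.
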